5.7 Restrictions

5.7.1 Prior Therapy/Washout Period

Subjects currently using ocular hypotensive medications must undergo a minimum washout period as specified in Table 1.

If washout is to be extended beyond 8 weeks (56 days) for logistical or other reasons, the Sponsor should be contacted.

Table 1 Ocular Hypotensive Medication Washout Period

Medication Class	Minimum Washout Period
Rho kinase inhibitor	6 weeks
Prostaglandins	4 weeks
β -adrenoceptor antagonists	4 weeks
Adrenergic agonists (including α -agonists such as brimonidine and apraclonidine)	2 weeks
Muscarinic agonists (e.g., pilocarpine), carbonic anhydrase inhibitors (topical or oral)	5 days

[Hughes 2005](#)

5.7.2 Fluid and Food Intake

On days that diurnal IOP measurements are made, subjects may not consume alcohol. Otherwise, there are no general restrictions on fluid or food intake for subjects participating in this study.

5.7.3 Subject Activity Restrictions

On days that diurnal IOP measurements are made, subjects may not engage in strenuous activity. In addition, eye dilation may cause blurred vision and temporary sensitivity to light. While pupils are dilated, subjects should protect eyes while in bright light by wearing sunglasses. Subjects should not drive or engage in any hazardous activity until vision returns to normal. Otherwise, there are no restrictions on subject activities during their participation in this study.

5.8 Treatment Compliance

All subjects will be instructed on the importance of following the once-daily dosing regimen. Dosing should occur in the evening between 20:00 and 22:00 hours. As no commercially available method is readily available for direct, single-container monitoring of treatment adherence with multi-dose ophthalmic products, no formal measure of treatment compliance is planned. Subjects should be reminded at all visits to dose every evening. In addition, subjects will be provided with dosing reminders.

5.9 Packaging and Labeling

The container-closure system for the netarsudil ophthalmic solution (0.01%, 0.02% or 0.04%) and netarsudil ophthalmic solution placebo in this clinical study is a white, multi-dose low density polyethylene (LDPE) dropper dose ophthalmic bottle with a polypropylene white cap. Each packaged unit will be labeled with an investigational label with the minimal information required per Japan regulatory requirements.

The products for each individual treatment assignment will be packaged into identical subject kits; each subject kit will contain one of 4 treatments: netarsudil ophthalmic solution 0.01%, 0.02% or 0.04% or netarsudil ophthalmic solution placebo.

5.10 Storage and Accountability

The study treatments must be dispensed or administered according to the procedures prescribed in this protocol. Only subjects enrolled in the study may receive study treatment, in accordance with all the applicable regulatory requirements. Only authorized staff is allowed to dispense these medications.

Under normal conditions of handling and administration, the study treatments are not expected to pose significant safety risk to site staff. Adequate precautions must be taken to avoid direct contact with the study treatment.

The study treatments will be stored in a secure area under the appropriate physical conditions for the product. Access to the study treatment will be limited to authorized site staff only. The study treatments will be stored as directed on the drug label. The study treatments should be stored refrigerated (2°C to 8°C/36°F to 46°F). Temperature of the study treatment storage location at the site is to be monitored using a calibrated monitoring device and documented.

At time of dispensing, the subject will be instructed to store the bottle(s) as directed on the drug label. Subjects should be instructed not to freeze the product.

5.11 Investigational Product Retention at Study Site

5.11.1 Receipt and Disposition of Study Medication

Study medication will be shipped to the Investigator's site from a central depot. The study medication storage manager at the Investigator's site will verify study medication shipment records by comparing the shipping documentation accompanying the study medication to the study medication actually received at the Investigator's site. If a discrepancy is noted, the appropriate individual at the Sponsor or designee must be notified immediately. The responsible person (e.g., study coordinator) at the Investigator's institution has to account for all used, partially used, and unused study medication. The responsible person will also maintain the drug accountability records.

5.11.2 Return of Study Medication

When the site is closed, the study is completed, or is terminated by the Sponsor; all study material including used and unused study medication will be returned to the Sponsor (or its designee). All study medication accounting procedures must be completed before the study is considered to be concluded. The responsible person at the Investigator's institution has to account for all used, partially used, and unused study medication. The study medication storage manager or designee will complete a study drug returns form or equivalent that will be signed by the Investigator or designee prior to returning the used and unused study medication to the Sponsor's designee.

6. STUDY PROCEDURES

6.1 Informed Consent

Prior to any study procedures, the study will be discussed with each subject. Subjects wishing to participate must give written informed consent. The verbal explanation of the study will cover all the elements specified in the written information provided for the subject. The Investigator will inform the subject of the aims, methods, anticipated benefits and potential hazards of the study, including any discomfort it may entail. The subject must be given every opportunity to clarify any points he/she does not understand and, if necessary, may ask for more information. At the end of the interview, the subject should be given time to reflect. Subjects and/or legally authorized representative then will be required to sign and date the informed consent form.

The informed consent form (ICF) must have received approval/favorable review by a properly constituted Institutional Review Board (IRB) or Independent Ethics Committee (IEC) prior to use. A copy of the signed and dated consent document will be given to each subject. The original signed and dated ICF must be maintained in the study files at the Investigator's site.

The Investigator or staff is responsible for ensuring that no subject is exposed to any study related examination or activity before the subject has given written informed consent. It should be emphasized that the subject is at liberty to withdraw consent to participate at any time, without penalty or loss of benefits to which the subject is otherwise entitled. Subjects who refuse to give, or withdraw, written informed consent may not be included or continued in this study, and should be notified that discontinuation from the study will not impact on their subsequent care.

6.2 Demographics and Medical History

Demographic data and any ongoing medication use will be collected and recorded. Any medications the subject took but discontinued within the 30 days prior to screening will also be recorded. Significant medical history will be collected and any current underlying medical conditions, including those that began within the last 30 days and which may have resolved before screening, additionally must be recorded.

6.3 Concomitant Medication Assessments

Use of all medications should be documented on the appropriate CRF. The site staff responsible for recording all concomitant medications will be identified on the Delegation of Responsibilities Log. Investigators are encouraged to contact the Sponsor/Sponsor representative for any questions regarding allowed medications. Judgment of continued study participation by the subject, and inclusion of this subject's subsequent visits in the safety and efficacy analysis will be made by the Sponsor.

6.4 Ophthalmic/Physical Assessment

The Investigator will review each subject's medical and ophthalmic history including systemic and ocular medication use to determine eligibility for this study. If enrolled, the Investigator will determine if there are any changes in health or concomitant medication use at each follow-up visit.

The Investigator or designee will also perform the following ophthalmic assessments as described in the Manual of Procedures (MOPs): VFQ-25, visual acuity, CS testing, visual field, IOP, biomicroscopy, central corneal thickness, gonioscopy, symptomatology, and dilated ophthalmoscopy.

The Investigator or designee will perform additional assessments for subjects with cornea verticillata as described in the MOPs: VFQ-25, CS testing and cornea verticillata grading

6.5 Dispensing Investigational Product

Study staff responsible for dispensing study medication will be listed on the Delegation of Responsibilities Log. When a subject meets all criteria for selection and has completed all screening assessments, the subject will be assigned to a treatment group according to the IWRS. The responsible study staff will account for used and unused investigation product by maintaining a study medication accountability log.

6.6 Efficacy Assessments

6.6.1 Specification of the Efficacy Parameters

The primary efficacy outcome will be the comparison of netarsudil ophthalmic solution (0.01%, 0.02% and 0.04%) relative to placebo for mean diurnal IOP within a treatment at Week 4 (Day 29) by Goldmann Applanation Tonometry.

Secondary efficacy outcomes will be comparison of netarsudil ophthalmic solution relative to placebo for:

- Mean diurnal IOP at Weeks 1 and 2 (Days 8 and 15, respectively)
- Mean change from baseline in mean diurnal IOP at each post-treatment visit
- Mean percent change from baseline in mean diurnal IOP at each post-treatment visit
- Mean IOP at each post-treatment time point
- Mean change from diurnally adjusted baseline IOP at each post-treatment time point
- Mean percent change from diurnally adjusted baseline IOP at each post-treatment time point

- Percentages of subjects achieving pre-specified mean, mean change, and percent mean change in mean diurnal IOP levels

Other secondary efficacy analyses may be carried out as described in the study Statistical Analysis Plan.

6.6.2 Method and Timing for Assessing, Recording, and Analyzing of Efficacy Parameters

As detailed in subsequent sections describing each visit and [Appendix 1](#), IOP will be measured at a screening visit, at 2 qualification visits after washout of ocular hypotensive medications as required, and at each post Day 1 treatment study visit.

6.7 Safety Assessments

The primary safety measures in both eyes of enrolled subjects will include:

- Ocular symptoms/adverse events
- VFQ-25 at baseline
- BCVA will be determined and completed prior to any IOP measurements.
- CS testing at baseline
- Objective findings of biomicroscopic examinations (i.e., anterior segment examinations including evaluation of cornea, conjunctiva, lids, and lens)
- Dilated ophthalmoscopy, including vertical cup-disc ratio measurements

Other safety assessments will be:

- Systemic safety assessments as measured by heart rate, blood pressure, and clinical laboratory evaluations (including hematology, clinical chemistry, and urinalysis)

For subjects who develop cornea verticillata, safety measures include:

- VFQ-25
- BCVA
- CS testing
- Cornea verticillata grading
- Time to cornea verticillata resolution

6.8 Adverse Events Assessments

6.8.1 Performing Adverse Event (AE) Assessments

Qualified study staff responsible for assessing adverse events (AEs) will be listed on the Delegation of Responsibilities Log. This includes assessment of AE severity and relationship to study medication. Adverse event information may be volunteered by the subject or solicited by study personnel through non-leading questions.

All AEs occurring during the study, regardless of the assumption of causal relationship, must be documented on the respective CRF. Adverse events should be documented from the time the subject receives the first dose of study medication until 30 days after the last dose of study drug.

If a subject has an ongoing AE at the time of study completion, the ongoing AE must be followed-up and provided appropriate medical care until the event has resolved or stabilized.

Documentation of AEs/adverse reactions includes start date and stop date, severity, action(s) taken, seriousness and outcome.

6.8.2 Adverse Event Definition

The following definitions of terms apply to this section:

- *Adverse event*. Any untoward medical occurrence associated with the use of a drug in humans, whether or not considered drug related.
- *Life-threatening AE or life-threatening suspected adverse reaction (SAR)*. An AE or SAR is considered “life-threatening” if, in the view of either the Investigator or Sponsor, its occurrence places the subject at immediate risk of death. It does not include an AE or SAR that, had it occurred in a more severe form, might have caused death.
- *Serious adverse event (SAE) or serious suspected adverse reaction (SSAR)*. An AE or SAR is considered “serious” if, in the view of either the Investigator or Sponsor, it results in any of the following outcomes: Death, a life-threatening adverse event, subject hospitalization or prolongation of existing hospitalization, a persistent or significant incapacity or substantial disruption of the ability to conduct normal life functions, or a congenital anomaly/birth defect. Important medical events that may not result in death, be life-threatening, or require hospitalization may be considered serious when, based upon appropriate medical judgment, they may jeopardize the subject and may require medical or surgical intervention to prevent one of the outcomes listed in this definition. Examples of such medical events include allergic bronchospasm requiring intensive treatment in an emergency room or at home, blood dyscrasias or convulsions that do not result in subject hospitalization, or the development of drug dependency or drug abuse.

- *Suspected adverse reaction (SAR)* means any AE for which there is a reasonable possibility that the drug caused the AE. For the purposes of CTN safety reporting, “reasonable possibility” means there is evidence to suggest a causal relationship between the drug and the AE. Suspected adverse reaction implies a lesser degree of certainty about causality than adverse reaction, which means any adverse event caused by a drug.
- *Unexpected AE or unexpected SAR.* An AE or SAR is considered “unexpected” if it is not listed in the Investigator’s Brochure or is not listed at the specificity or severity that has been observed. For example, under this definition, hepatic necrosis would be unexpected (by virtue of greater severity) if the [Investigator’s Brochure](#) referred only to elevated hepatic enzymes or hepatitis. Similarly, cerebral thromboembolism and cerebral vasculitis would be unexpected (by virtue of greater specificity) if the Investigator’s Brochure listed only cerebral vascular accidents. “Unexpected,” as used in this definition, also refers to AEs or SARs that are mentioned in the Investigator’s Brochure as occurring with a class of drugs or as anticipated from the pharmacological properties of the drug, but are not specifically mentioned as occurring with the particular drug under investigation.

Note: Any medical condition present prior to administration of the masked study medication which remains unchanged or improved should not be recorded as an AE at subsequent visits.

Note: If an event occurs during the washout period (prior to subject enrollment and the commencement of study medication), it should be recorded as part of the Medical History and not as an AE. As noted in Section 7.3.1, any change in their Visit 1 (Screening) health status prior to enrollment should be recorded on the Medical History page of the CRF.

Note: In the present study, Investigators are asked to use the verbatim term “conjunctival hyperemia” on the study AE form to describe observations of conjunctival redness if the ocular redness observation is increased from Visit 1 (Screening) observations and clinically meaningful. Investigators are also asked to note all observations of conjunctival hyperemia on the biomicroscopy CRF as well as on the study AE form.

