Subjects will return to the Investigator's office. The subject will be questioned about any missed doses and any changes in their health or concomitant medication use. Subjects will be examined, and each examination will include:

- Heart rate and blood pressure
- Symptomatology: Individuals will be asked "How are you feeling?"
- Recording of any AEs
- BCVA
- A non-dilated eye examination will be performed, including IOP measurements and biomicroscopy. IOP must be measured between 09:00 and 09:30 hours.

After randomization, any new or worsening of symptoms are to be entered as AEs.

Subjects are allowed to leave the Investigator's office between assessments and eat and drink without restrictions. However, subjects are not to consume alcohol or engage in strenuous exercise.

7.3.5 Visit 4.1 (Week 1 [Day 8], for IOP and safety measurements at 11:00 hours)

Subjects will be examined, and each examination will include:

- Symptomatology: Individuals will be asked "How are you feeling?"
- Recording of any AEs
- A non-dilated eye examination will be performed, including IOP measurements and biomicroscopy. IOP must be measured between 11:00 to 11:30 hours.

Subjects are allowed to leave the Investigator's office between assessments and eat and drink without restrictions. However, subjects are not to consume alcohol or engage in strenuous exercise.

7.3.6 Visit 4.2 (Week 1 [Day 8], for IOP and safety measurements at 16:00 hours)

Subjects will be examined, and each examination will include:

- Symptomatology: Individuals will be asked “How are you feeling?”
- Recording of any AEs.
- A non-dilated eye examination will be performed, including IOP measurements and biomicroscopy. IOP must be measured between 15:30 and 16:30 hours.

Subjects will be:

- Instructed to continue to administer their study medication at home between 20:00 - 22:00 hours (taking the daily evening dose on that day)
- Instructed to return to the office with their used study medication on Week 2 (Day 15)

7.3.7 Visit 5.0 (Week 2 [Day 15], for IOP and safety measurements at 09:00 hours)

Subjects will return to the Investigator’s office. The subject will be questioned regarding any missed doses and any changes in their health or concomitant medication use. Subjects will be examined, and each examination will include:

- Heart rate and blood pressure
- Symptomatology: Individuals will be asked “How are you feeling?”
- Recording of any AEs
- BCVA

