- A non-dilated eye examination will be performed, including IOP measurements and biomicroscopy. IOP must be measured between 09:00 and 09:30 hours.

Any new or worsening of symptoms beyond those collected at baseline are to be entered as AEs.

Subjects are allowed to leave the Investigator’s office between assessments and eat and drink without restrictions. However, subjects are not to consume alcohol or engage in strenuous exercise.

7.3.8 Visit 5.1 (Week 2 [Day 15], for IOP and safety measurements at 11:00 hours)

Subjects will be examined, and each examination will include:

- Symptomatology: Individuals will be asked “How are you feeling?”

- Recording of any AEs
- A non-dilated eye examination will be performed, including IOP measurements and biomicroscopy. IOP must be measured between 11:00 to 11:30 hours.

Subjects are allowed to leave the Investigator's office between assessments and eat and drink without restrictions. However, subjects are not to consume alcohol or engage in strenuous exercise.

7.3.9 Visit 5.2 (Week 2 [Day 15], for IOP and safety measurements at 16:00 hours)

Subjects will be examined, and each examination will include:

- Symptomatology: Individuals will be asked "How are you feeling?"
- Recording of any AEs
- A non-dilated eye examination will be performed, including IOP measurements and biomicroscopy. IOP must be measured between 15:30 and 16:30 hours.

Subjects will be:

- Instructed to continue to administer their masked medication at home between 20:00 - 22:00 hours (taking the daily evening dose on that day)
- Instructed to return to the office with their study medication on Week 4 (Day 29)

7.3.10 Visit 6.0 (Week 4 [Day 29], for IOP and safety measurements at 09:00 hours)

Subjects will return to the Investigator's office. The subject will be questioned about any missed doses and any changes in their health or concomitant medication use. Subjects will be examined, and each examination will include:

- Heart rate and blood pressure
- Symptomatology: Individuals will be asked "How are you feeling?"
- Recording of any AEs
- Urine pregnancy test (tests for applicable female subjects of child bearing potential may be performed at any time point throughout Visit 6)
- Blood samples will be taken for clinical chemistry and hematology, and a urine sample will be taken for urinalysis (samples may be taken at any time point throughout Visit 6)
- BCVA

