8.3 Definition of Baseline

For diurnally-adjusted IOP, baseline will refer to the time-relevant measure at Visit 3 (e.g., IOP at 09:00 hours at Visit 3.0 will be the baseline for 09:00 hours at Visit 4.0, Visit 5.0 and Visit 6.0; etc.). For all other variables, baseline is defined as the last measurement prior to the first dose of study drug. An additional definition of baseline for conjunctival hyperemia will also be used: baseline (pre-washout) will be defined as the conjunctival hyperemia measure at Visit 1. Change from baseline will be calculated as: Follow-up Visit – Baseline Visit.

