15.1 Adverse Events

An AE is defined as any untoward medical occurrence associated with the use of a drug in humans, whether or not the event is considered drug-related. All AEs occurring during the study, regardless of the assumption of causal relationship, must be documented on the respective CRF. AEs should be

documented from the time the subject receives the first dose of study drug until 30 days after the last dose of study drug.

Treatment-emergent adverse events (TEAEs) are defined as any event that occurs or worsens on or after the day that randomized study treatment is initiated, and by study completion date.

Adverse events are coded using the MedDRA/J, Version 21.1. An overall summary will be presented to report the number of events and incidents of subjects having at least one event in the following categories:

- TEAEs
- Ocular TEAEs
- Non-ocular TEAEs
- Serious TEAEs
- Treatment-related TEAEs (reported as possibly related or related to the study drug)
- Treatment-related serious TEAEs
- TEAEs by maximum severity
- TEAEs leading to study drug discontinuation
- TEAEs resulting in death

Separate summaries will be provided for the number and percentage of TEAEs by SOC and PT for the following categories as well as the p-values for comparing the incidence between each netarsudil (0.01%, 0.02%, and 0.04%) group and placebo:

- Ocular TEAEs
- Non-ocular TEAEs
- Serious TEAEs
- Treatment-related TEAEs (reported as possibly related or related to the study drug)

If a subject reports the same PT multiple times within the same SOC, that PT will only be reported once within that SOC. As with the PT, if a subject reports multiple conditions within the same SOC, that SOC will only be reported once. In the summary, SOC will be listed in ascending alphabetical order; PTs will be listed in order of descending frequency within each SOC.

Treatment-emergent AEs will also be summarized by SOC, PT, and maximum severity. If a subject experiences more than one AE within SOC or PT, that subject will be counted only once for that event under the maximum severity.

All AEs will be presented in a subject listing. In addition, all serious AEs and AEs leading to study drug discontinuation will be listed separately.

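### Protocol 6.8.2 gives two inconsistent adverse-event instructions for conjunctival hyperemia, one of them using a pre-washout comparator that conflicts with the pre-dose rules elsewhere in the plan

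*Protocol*

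**What the plan says.** A note in Protocol 6.8.2 asks for the verbatim term conjunctival hyperemia on the AE form "if the ocular redness observation is increased from Visit 1 (Screening) observations and clinically meaningful". Its next sentence reads: "Investigators are also asked to note all observations of conjunctival hyperemia on the biomicroscopy CRF as well as on the study AE form".

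Visit 1 is the visit before washout. SAP 8.3 says so for this variable: "baseline (pre-washout) will be defined as the conjunctival hyperemia measure at Visit 1". Protocol 9.1 has the same definition. It is an additional one; for variables other than diurnally adjusted IOP the main rule is that "baseline is defined as the last measurement prior to the first dose of study drug".

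The other AE rules look to the state before dosing:

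- Protocol 6.8.2, an earlier note: "Any medical condition present prior to administration of the masked study medication which remains unchanged or improved should not be recorded as an AE".
- Protocol 7.3.4 (Week 1): "After randomization, any new or worsening of symptoms are to be entered as AEs".
- Protocol 7.3.7 (Week 2) and 7.3.10 (Week 4): "Any new or worsening of symptoms beyond those collected at baseline are to be entered as AEs".
- SAP 15.1 defines a treatment-emergent AE (TEAE) as "any event that occurs or worsens on or after the day that randomized study treatment is initiated", up to study completion.

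Protocol 6.14 has the conjunctiva examined in both eyes at every visit. SAP 15.3 summarizes the hyperemia score as change from baseline and from Visit 1. It also tabulates, with Fisher's exact tests, the incidence of at least one grade increase from baseline in biomicroscopy findings. The SAP table list adds Table 14.3.3.5 (clinically significant increase from baseline in hyperemia) and Table 14.3.3.6 (at least one grade increase).

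**The concern.** Subjects on glaucoma drops at Visit 1 stop them for a minimum of 5 days to 6 weeks, depending on drug class (Protocol 5.7.1). Redness can change in that time. The hyperemia exclusion (Protocol 4.3, criterion 3) applies at Qualification Visit #2 only, so it limits the Day 1 grade but not the Visit 1 grade. A subject's Visit 1 grade can therefore be higher than the grade from which study treatment starts.

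Hyperemia matters more here than most AEs. Protocol 1.3 reports it in 53% of patients on the once-daily 0.02% product, and Protocol 6.8.6 names it the most frequent AE. Safety relative to placebo is a primary objective, the study title includes finding the optimum concentration, and TEAE incidence is to be tested for each concentration against placebo (Protocol 9.7.2, SAP 15.1). If the AE form is filled in under different rules at different places, that incidence has no single meaning.

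**Working it through.** The plan gives no figure for this rule, so the main check is textual. Protocol 4.3 shows that moderate is +2 and severe +3; the grades 0 and 1 used below are examples.

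**Step 1. Apply each rule to the same grade paths** (Visit 1 / last pre-dose / on treatment). "Yes" under a comparator assumes that the redness is also judged clinically meaningful.

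| Path | Increase over Visit 1 (6.8.2, trigger) | All observations (6.8.2, next sentence) | Worse than pre-dose (6.8.2 earlier note, visit rules, SAP 15.1) | Grade increase from baseline (Table 14.3.3.6) |
|---|---|---|---|---|
| 0 / 0 / 1 | Yes | Yes | Yes | Counted |
| 1 / 0 / 1 | No | Yes | Yes | Counted |
| 0 / 1 / 1 | Yes | Yes | No | Not counted |
| 1 / 1 / 1 | No | Yes | No | Not counted |

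The rules agree only in the first path. In the second, redness fell during washout and came back on treatment: this meets the SAP definition of a TEAE but not the Visit 1 trigger. In the third, redness rose before any dose: it meets the trigger, although the earlier note in 6.8.2 says an unchanged pre-existing condition is not an AE. In the fourth, nothing changed, yet the all-observations sentence would put it on the AE form. The error can run in either direction.

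**Step 2. Who can be affected.** The two comparators differ only where the Visit 1 and last pre-dose grades differ. The under-count arises in washed-out subjects whose redness fell. Treatment-naive subjects are eligible (Protocol 4.2, criterion 3) and have no washout. The rule is the same in every arm, placebo included.

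**Step 3. Illustration of the under-count alone.** Let w be the share of would-be hyperemia cases who were washed out, and m the share of those whose on-treatment redness does not exceed their Visit 1 grade. Under a strict Visit 1 comparator:

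recorded rate = 0.53 × (1 − w × m); events lost per arm of 52 = 52 × 0.53 × w × m.

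The 53% comes from Protocol 1.3 and the 52 from Protocol 9.2. **The values of w and m are assumptions; the documents give neither.** The last column is the power of a two-sided Fisher test with 52 per arm, with an assumed 10% placebo rate reduced by the same factor.

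| w | m | Recorded rate | Events lost per 52 | Fisher power |
|---|---|---|---|---|
| 0 | any | 53.0% | 0 | 0.998 |
| 0.25 | 0.10 | 0.53 × 0.975 = 51.7% | 0.7 | 0.997 |
| 0.50 | 0.25 | 0.53 × 0.875 = 46.4% | 3.4 | 0.992 |
| 1 | 0.50 | 0.53 × 0.50 = 26.5% | 13.8 | 0.825 |

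In the middle case the difference from placebo shrinks from 43.0 to 43.0 × 0.875 = 37.6 percentage points, and the test is hardly touched. With a pre-dose comparator, w × m drops out and this loss is zero. The table ignores the opposite error in the third and fourth paths.

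**The case against.** The strongest reply is that the finding is not lost. Every observation goes on the biomicroscopy CRF, and SAP 15.3 and Tables 14.3.3.5 and 14.3.3.6 report increases from baseline as incidence. The subject graded 1, then 0, then 1 is counted in Table 14.3.3.6. **This stands.** A reader might infer that drug-induced redness goes unrecorded, or that hyperemia becomes an AE only if it exceeds the Visit 1 grade. The documents do not support either: the next sentence of the note asks for all observations on the AE form, and Protocol 6.8.1 requires all AEs to be documented.

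The reply does not reach the AE tables. Severity, relatedness and action taken are collected through AE reporting (Protocol 6.8.3 to 6.8.5) and feed the summaries in SAP 15.1. An event absent from the AE form cannot enter them. SAP 15.3 also does not define the clinically significant increase counted in Table 14.3.3.5.

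The all-observations sentence could be read as covering only observations that already meet the trigger. The text does not say so, and on that reading the comparator conflict would remain.

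Visit 1 is a declared second baseline for this variable, so it is not a slip of the pen. That is true for the score summaries, but neither document extends it to the TEAE definition. It is also fair that the visit-level rules speak of symptoms, not slit-lamp grades; the earlier note in 6.8.2 and SAP 15.1 are not limited in that way.

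Randomization is stratified by site, so differences in recording between sites should be spread over the arms. This limits bias in the comparison, but does not make the reported rates interpretable.

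**Conclusion.** The point holds as an inconsistency in the AE-recording rules. The two sentences of the note give different AE-form instructions, and the Visit 1 comparator conflicts with the pre-dose comparator in the earlier note, the visit-level rules and the SAP's TEAE definition. With about 30 sites, hyperemia AE counts may mix definitions. They may be too low in washed-out subjects whose redness fell before Day 1, and too high where it rose before dosing or where unchanged redness is entered.

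Neither the net direction nor the size is known. The range of 51.7% to 26.5% rests on assumed w of 0.25 to 1 and m of 0.10 to 0.50. It also assumes that the earlier 53% would apply here under a pre-dose comparator; the documents do not say which comparator the earlier studies used.

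A reader might infer more, but the documents do not support it:

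- An established under-count of a given size: nothing gives the share of cases lost.
- Little effect on placebo: the same rule applies in all arms.
- Faulty attribution of discontinuations: the primary reason for discontinuation is captured separately (SAP section 9).

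The protocol reviewed is Amendment 1, while the SAP cites Amendment 2. Whether the later amendment changed this note should be checked first.

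**What to change.** Reconcile both sentences of the hyperemia note in Protocol 6.8.2:

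1. Make the AE-form trigger a clinically meaningful increase from the last pre-dose grade at Visit 3. Under the SAP 8.3 rule this is the Visit 3.2 examination at 16:00 on Day 1, the last biomicroscopy before the first evening dose.
2. Ask for all observations of hyperemia on the biomicroscopy CRF, and on the AE form only when the trigger is met. Changing the comparator alone would leave the note in conflict with itself.
3. Keep change from Visit 1 as the additional descriptive summary already in SAP 15.3.

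The cost is one amended note or a memo to sites. No visit or examination is added. Recorded AE rates may change somewhat, in either direction. Entries never made on the AE form are hard to reconstruct later, so the change is worth most before subjects are dosed.
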